Based on a strong body of empirical work demonstrating the benefits of HRVB in reducing anxiety (Henriques, Keffer, Abrahamson, & Horst 2011) and depressive symptoms (Patron et al., 2013; Rene, 2008) a secondary aim of this proposal is to evaluate the efficacy of HRVB-SCT in improving smoking and emotional health outcomes among adults who smoke. Transdiagnostic processes that promote avoidance and escape of emotional distress are implicated in the development and maintenance of cigarette smoking dependence (Baker, Piper, [name], Majeskie & Fiore, 2004), and may also explain why individuals with depressive and anxiety symptoms are more susceptible to cigarette smoking dependence and poor cessation outcomes (Leventhal & Zvolensky, 2015). Existing smoking cessation interventions informed by these models largely rely upon cognitive-behavioral strategies (Gifford, Kohlenberg, Hayes, et al., 2011; Brown, Reed, Bloom, et al., 2013.) However, automatic visceral responses to emotional distress may impede the utilization of intentional self-control strategies. Biobehavioral interventions that directly address transdiagnostic physiological processes may offer a more targeted means of improving outcomes, thereby identifying an alternative treatment mechanism. Moreover, the development of biobehavioral interventions may improve smoking cessation outcomes for smokers with moderate emotional distress who are not responsive to, or are less receptive of, cognitivebehavioral interventions.

The proposal will use a staged model for developing and standardizing behavioral interventions, as indicated by NIDA. The first phase (i.e., Phase 1A) of the project has focused on drafting, piloting, and modifying an integrated HRVB smoking cessation treatment (HRVB-SCT). The second phase of the project (Phase 1B) will focus on assessing the acceptability and feasibility of treatment delivery, fidelity, and potential for improving smoking cessation outcomes and reducing emotional distress. Data collected during this time will also potentially inform a larger R01 application of a RCT of HRVB-SCT to evaluate smoking and emotional distress outcomes and explore transdiagnostic physiological and cognitive-affective treatment mechanisms.

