1.5 Sample Size Justification

Given the developmental nature of the project, our sample size was selected to obtain a reasonable estimate of treatment feasibility, acceptability, and efficacy that would be critical to supporting a future R01 clinical trial. We enrolled n=10 participants for phase 1A and plan to enroll n=30 for phase 1B. Statistical power for phase 1B was determined using G*Power 3.1.9. and based on the analytic approach for examining our secondary outcomes of interest. Separate paired sample t-tests will be used to examine within-subject differences in the number of cigarettes smoked per day and in emotional distress from pretreatment baseline, 1-month post-quit, and 3-month post-quit, respectively. Paired sample t-tests determined that at a power of 80%, α =0.25, an N=30 is sufficient to detect a small to medium-sized effect (Cohen's d=0.40). A Type I error rate of .25, has been suggested as an adequate error rate for testing preliminary pilot study effects and can be used to inform a more comprehensive study, including sample size planning for a future Stage II R01 (Moore et al., 2011). Given our relatively short assessment phase, this may still be too conservative estimate. Therefore, we will carefully examine effect size estimates and pursue a larger trial if a small to medium effect is observed.

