1.6 Study Variables and Outcomes

To inform a subsequent clinical trial, our analytic plan focuses on the use of descriptive and inferential statistics.

Primary Outcomes:

9/17/2024

Aims 1.a. and 1.b.: Feasibility and Acceptability:

Descriptive statistics will be used to assess feasibility and acceptability of HRVB (see 1.a. Intervention feasibility and 1.b. Intervention acceptability). Ratings of perceived effectiveness, appropriateness, satisfaction, and ease of the intervention are made on a 5-point Liker-type scale ranging from 0-completely disagree to 4-completely agree. Descriptive statistics will also be used to assess participant attendance, adherence, indexed by time spent using the intervention. Instances of technological limitations will be indexed both by count as well as qualitative descriptors (e.g., inner balance device failure to pick up recording; Bluetooth connection errors, etc.).

Secondary Outcomes:

Aim 2.a: Changes in smoking behavior:

Descriptive statistics will be used to report total number and percent of participants reporting abstinence on their quit day using the intent-to-treat sample as well as those who remain in treatment.

Sustained smoking cessation will be assessed descriptively using point prevalence abstinence defined by self-reported abstinence verified by both carbon monoxide analysis of breath sample and saliva cotinine. Paired sample t-tests will be used to assess changes in smoking rate within participants from baseline to quit day, two-week, one-month, and three-month follow-up, as a proxy for harm reduction.

Aim 2.b.: Changes in emotional distress:

Paired sample t-tests will be used to assess changes in emotional distress, including depression, anxiety and stress, within participants, from baseline to two-week, one-month, and three-month follow-up.

We will also examine correlations between baseline emotional distress ratings and key outcomes, including feasibility and acceptability ratings, changes in smoking behavior, and emotional distress to evaluate whether the intervention may be particularly beneficial for smokers with elevated emotional distress.

The following list of measures will be used to assess primary and secondary outcomes of interest:

1.a: Intervention feasibility

| Outcome | Method | Time Frame |
|------------------------|---|-------------------------------------|
| Participant Attendance | Number of attended sessions out of 7 possible | 7 weeks |
| | sessions | |

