| Practice Adherence | Time (in minutes) spent practicing the breathing | 7 weeks |
| | intervention | |
| Intervention | Participant self-report items assessing how effective | Week 1 (i.e., treatment initiation) |
| Effectiveness | the intervention was in helping participants quit and | and Week 16 (i.e., 3-MFU) |
| | manage emotional distress | |
| Intervention | Participant self-report items assessing intervention | Week 1 (i.e., treatment initiation) |
| Appropriateness | comprehension and fit | and Week 16 (i.e., 3-MFU) |
| Intervention Ease | Participant self-report items assessing ease of use | Week 1 (i.e., treatment initiation) |
| | and fit into daily lifestyle | and Week 16 (i.e., 3-MFU) |
| Technological | Interventionist self-report items assessing incidences | 7 weeks |
| Limitations | of technical issues and related effects on intervention | |
| | delivery | |

1.b. Intervention acceptability

9/17/2024

| Outcome | Method | Time Frame |
|-------------------------|---|---|
| Satisfaction and Liking | Self-report items assessing satisfaction with learning the intervention, liking the intervention, breathing techniques, nicotine replacement, and recommending the intervention to others | Week 1 (i.e., treatment initiation) and Week 16 (i.e., 3-MFU) |

2. Secondary Outcome Measures:

2.a. Changes in smoking behavior

| Outcome | Method | Time Frame |
|--------------------------------|---|---|
| Quit-day abstinence | Self-reported abstinence on Quit Day, verified with carbon monoxide analysis of breath sample (CO < 8ppm) | Week 3 (i.e., Quit Date) |
| Sustained Smoking Cessation | Self-reported abstinence, verified carbon monoxide analysis, and salivary cotinine (<10 ng/mL) at study termination | Week 16 (i.e., 3-MFU) |
| Smoking rate | Timeline Followback interview assessing changes in smoking rate | Week 0 (i.e., Baseline,) Week 3 (i.e., Quit Date), 5 (i.e., 2-WFU), Week 7 (i.e.,1-MFU) and Week 16 (i.e., 3-MFU) |

2.b: Changes in emotional distress (i.e., anxiety, depression, and stress)

| Outcome | Method | Time Frame |
|--------------------|--|--|
| Emotional Distress | Self-report items assessing past 2-week ratings of depression, anxiety, and stress | Week 0 (i.e., Baseline,) Week 5 (i.e., 2-WFU), Week 7 (i.e.,1-MFU) and Week 16 (i.e., 3-MFU) |

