6.4 Data Management Plan

6.5 Data Analysis

Primary analyses will use descriptive statistics to assess feasibility and acceptability of HRVB. Ratings of perceived effectiveness, appropriateness, satisfaction, and ease of intervention are made on a 5-point Liker-type scale ranging from 0-completely disagree to 4-completely agree. Descriptive statistics will also be used to assess participant attendance, adherence, indexed by time spent using the intervention. Instances of technological limitations will be indexed both by count as well as qualitative descriptors (e.g., inner balance device failure to pick up recording; Bluetooth connection errors, etc.) Secondary analyses for Aim 2.a: Changes in smoking behavior will include descriptive statistics used to report total number and percent of participants reporting abstinence on their quit day using the intent-to-treat sample as well as those who remain in treatment. Sustained smoking cessation will be assessed descriptively using point prevalence abstinence defined by self-reported abstinence verified

9/17/2024

by both carbon monoxide analysis of breath sample and saliva cotinine. Paired sample t-tests will be used to assess changes in smoking rate within participants from baseline to quit day, two-week, one-month, and three-month follow-up, as a proxy for harm reduction. Secondary analyses for Aim 2.b: Changes in emotion distress will include paired sample t-tests used to assess changes in emotional distress, including depression, anxiety and stress, within participants, from baseline to two-week, one-month, and three-month follow-up. To explore whether the intervention may be particularly beneficial for smokers with elevated emotional distress, we will examine correlations between baseline emotional distress ratings and key outcomes, including feasibility and acceptability ratings, changes in smoking behavior, and emotional distress.

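### The correlation of baseline distress with change in smoking rate is not adjusted for baseline cigarettes per day and may mislead if change is an absolute difference and distress is related to baseline smoking

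*Combined protocol and SAP*

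**What the plan says.** Section 1.6 (Secondary Outcomes, end of Aim 2.b) states: "We will also examine correlations between baseline emotional distress ratings and key outcomes, including feasibility and acceptability ratings, changes in smoking behavior". The purpose given is "to evaluate whether the intervention may be particularly beneficial for smokers with elevated emotional distress". Section 6.5 repeats the analysis and marks it as exploratory: "To explore whether the intervention may be particularly beneficial for smokers with elevated emotional distress". Neither section names a covariate, a partial correlation, a regression or a scale of change.

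For smoking rate, the main analysis is a within-person comparison: "Paired sample t-tests will be used to assess changes in smoking rate within participants from baseline to quit day". The power statement in section 1.5 refers to "within-subject differences in the number of cigarettes smoked per day and in emotional distress". The natural reading of change is therefore an absolute difference in cigarettes per day, although neither section says so for the correlation.

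The baseline rate is available. The outcome table in section 1.6 lists "Timeline Followback interview assessing changes in smoking rate", with Week 0 among the time points. No planned analysis uses it as a covariate.

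On how distress relates to smoking at entry, section 1.2 says only that "individuals with depressive and anxiety symptoms are more susceptible to cigarette smoking dependence and poor cessation outcomes". It gives no correlation with cigarettes per day.

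**The concern.** An absolute reduction is tied to the starting value. Someone who smokes 30 a day and quits scores a reduction of 30; someone who smokes 6 and quits scores 6. The two responded equally well. If distressed participants tend to start higher, distress will correlate with larger reductions even when proportional response has nothing to do with distress. If they tend to start lower, a real advantage can be hidden.

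The eligibility criteria set a floor of 5 cigarettes per day and no ceiling, so baseline rates can vary widely. Distress is not an entry criterion, so these correlations are the only planned look at whether more distressed smokers do better. Smokers with emotional distress are the group that motivates the project in section 1.2, and the pilot is meant to inform a larger trial.

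**Working it through.** **The plan's own figure.** Section 1.5 gives N = 30, 80% power, alpha 0.25 and d = 0.40 for a paired t-test. By the exact noncentral t with two-sided alpha 0.25, d = 0.40 needs N = 26, and N = 30 gives about 85% power. So 30 is sufficient, as the text says. This figure does not cover the correlation, for which the plan states neither power nor alpha.

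**Formula.** Let D be baseline distress, B baseline cigarettes per day and C the absolute reduction. If C is unrelated to D given B, and the relations are linear,

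r(D, C) = r(D, B) × r(B, C).

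The second factor is positive because C cannot exceed B and equals B in quitters. The first factor is unknown, so it is varied.

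**Simulation, first set of assumptions** (none is from the documents except n = 30 and the floor of 5). Baseline is lognormal with mean 15 and SD 7, floored at 5. Thirty percent quit, and the rest cut by about 40% (SD 20 points). Response is independent of distress. There are 20,000 trials per setting. Here rho is the assumed correlation of distress with log baseline rate. The last two columns give the share of trials with a significant result in the direction of more benefit at two-sided alpha 0.25, where the nominal share is 12.5%.

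| rho | mean r, unadjusted | more benefit, unadjusted | more benefit, adjusted for baseline |
|---|---|---|---|
| 0 | 0.00 | 12% | 13% |
| 0.1 | 0.05–0.06 | 19–20% | 12–13% |
| 0.2 | 0.11 | 29–30% | 12–13% |
| 0.3 | 0.17 | 40–41% | 12–13% |
| 0.4 | 0.22–0.23 | 53–54% | 12–13% |

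Ranges reflect repeated runs. The formula agrees. At rho = 0.3 the realised r(D, B) is 0.282 and r(B, C) is 0.582, and 0.282 × 0.582 = 0.16. At rho = -0.2 the sign reverses: mean r is -0.11 and the favourable share falls to 4%.

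**Second set of assumptions.** Baseline mean is 14, SD 6.6 and minimum 5. Between 20% and 80% quit, and the others keep 50–80% of baseline. Then r(B, C) runs from 0.32 to 0.84. The spurious r is 0.06–0.15 at rho = 0.2 and 0.09–0.23 at rho = 0.3. The favourable shares at alpha 0.25 are 21–37% and 26–55%. At alpha 0.05 (nominal 2.5%) they are 5–13% and 7–24%. Adjustment restores the nominal rate throughout.

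**If distress also lowers quitting.** With the first set, rho = 0.2 and an assumed odds ratio of 1.5 per SD of distress against quitting, the raw mean r is about 0.00. The adjusted value is about -0.14. The raw analysis shows nothing where there is a poorer response, and the adjusted analysis recovers it.

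**Scale.** Percent change, unadjusted, also holds the favourable share at 12–13%. Both simulations assume proportional reduction, however, which favours that scale.

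**The case against.** A reader might infer that distressed smokers will appear to benefit more. The documents do not support that. They give no correlation between distress and cigarettes per day. Section 1.2 speaks of dependence, and section 4.3 C suggests that other indicators may capture dependence better than the amount smoked. The same sentence in section 1.2 also predicts poorer cessation, which pulls the other way and can cancel the artefact in the raw figure. This objection stands against any fixed direction. It does not rescue the unadjusted correlation, which would then blend two opposing effects.

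The scale is also not fixed. Aim 2.a covers quit-day abstinence, sustained cessation and smoking rate; the first two are yes/no outcomes and not bounded by the baseline rate. This stands and confines the point to smoking rate.

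It can be argued that a larger absolute reduction is a larger benefit, since the plan treats smoking rate as a stand-in for harm reduction. That is a legitimate quantity, but it answers a different question from whether distressed smokers respond better from a given starting rate. The plan should say which it means.

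Alpha 0.25 is stated only for the paired t-tests. The rejection shares above borrow it; the bias in r does not depend on it. For comparison, the standard error of r at n = 30 is about 1/√29 = 0.19, so the artefact at rho up to 0.3 is within one standard error.

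A reader might also infer that this correlation will select the population of the larger trial. No decision rule uses it. Section 1.5 ties the larger trial to observed effect sizes, and section 6.5 calls the analysis exploratory.

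**Conclusion.** The point holds conditionally, and for smoking rate only. The unadjusted correlation may mislead if change is an absolute difference in cigarettes per day and if distress is correlated with the baseline rate. With a positive correlation it overstates benefit in distressed smokers or masks a poorer response; with a negative one it does the reverse; at zero there is no bias. For assumed correlations of 0.1 to 0.4 the spurious mean r is about 0.06 to 0.23. That range rests on assumed baseline spread, quit rates and proportional reductions, none of which the documents supply.

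This is a minor, nearly free improvement to an exploratory analysis. It would be too much to conclude that adjustment lets the trial show differential efficacy. The design is a single-arm open pilot, so even the adjusted association shows who does better, not in whom the intervention works better.

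**What to change.** In sections 1.6 and 6.5, for the smoking-rate outcome only:

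- State the scale of change and the follow-up time points used.
- Replace the raw correlation by an association adjusted for baseline cigarettes per day from the Timeline Followback. This can be a partial correlation, or a regression of follow-up rate on baseline distress and baseline rate. Report the estimate with a confidence interval.
- Describe the result as an exploratory prognostic association that cannot, without a control arm, show a greater effect of the intervention in distressed smokers.

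If total absolute reduction is also of interest for harm reduction, the raw figure can be shown beside the adjusted one and labelled as such.

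The cost is one covariate already collected and one degree of freedom (27 instead of 28 at n = 30). Only the analysis text changes; visits, measures and sample size stay as they are.

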1.1 Purpose/Specific Aims

The purpose of the study is to conduct an open trial assessing the feasibility and acceptability of a refined heart rate variability biofeedback as a smoking cessation treatment adjunct for individuals who smoke cigarettes.

A. Objectives

The present investigation is an open pilot trial assessing the acceptability and feasibility of a heart rate variability (HRV) biofeedback smoking cessation treatment (HRVB-SCT) for individuals who smoke cigarettes. Primary significant findings will support the integration of HRVB as an acceptable and feasible treatment adjunct to standard smoking cessation treatment. Secondary significant findings will support the expansion of HRVB as a transdiagnostic treatment adjunct that alters cardiac vagal functioning to promote smoking cessation outcomes and emotional and behavioral regulation. Together, primary and secondary findings will support changes to the status quo of cognitive-behavioral intervention approaches and decrease the health and economic burden of smokers who suffer from emotional distress.

The goals are to: (a) assess the acceptability and feasibility of the HRVB intervention as an treatment adjunct to SCT (b) assess changes in smoking behavior and emotional distress and (c) collect additional information to assist in further refining the intervention for a larger R01 RCT.

B. Hypotheses / Research Question(s)

- Primary Analysis: To complete a pilot open trial analyzing the feasibility and acceptability of HRVB-SCT. Intervention feasibility and acceptability will be indexed by measures of i participant attendance and practice adherence, participant self-report ratings of intervention satisfaction, effectiveness, appropriateness, and ease, and therapist reported technological limitations.
- 2. Secondary Analysis: To examine whether smokers receiving HRVB-SCT evidence improvements in: (1) smoking behavior as indexed by self-reported quit-day abstinence, verified by carbon monoxide breath analysis (CO<8ppm); sustained smoking cessation, verified by CO and salivary cotinine levels (<10ng/mg); and self-reported reductions in smoking rate and (2) emotional distress as indexed by self-reported anxiety, mood, and stress ratings. We expect HRVB-SCT will be associated with significant improvements in smoking and emotional health outcomes.

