Smoking Cessation Treatment (SCT): All participants will receive six smoking cessation counseling sessions lasting approximately 20-30m each. The first will also occur in-person, after the baseline portion of the initial in-person baseline assessment. In total, participants will complete two in-person SCT sessions (Sessions 1 and 7) and four remote teletherapy sessions via Zoom (Sessions 2-5; see *Table 1*). Trained research personnel providing SCT will use a protocol adapted from the National Cancer Institute's *Clear Pathways* guide. Each participant will be provided with an adapted version of *Clear Pathways* and be given weekly assignments. Participants will receive an 8-week supply of transdermal Nicotine Replacement Therapy (NRT) patches, at their in-person baseline visit. Smoking cessation counselors will provide remote instruction and feedback on NRT use. Specifically, participants will be instructed to place their first nicotine patch upon waking on their quit day (Fiore et al., 2008). Participants who smoke ≥ 10 cigarettes daily will begin with a 2-week course of 21 mg patch, followed by 4-week taper of 2-weeks of the 14mg and 2-weeks of the 7mg patch. We will recommend that patients who smoke 5-9 CPD begin with the 14 mg patch, as indicated by clinical practice guidelines.

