1.4 Preliminary Data

Complete reporting of preliminary data collected during the Pilot Phase IA of this trial can be found under the eIRB protocol Pro2018001848. Of particular relevance for the current protocol, feasibility findings from the preliminary Phase 1A of this study suggest the previous in-person structure could be improved. Primary Phase IA outcome measures assessing intervention feasibility included participant attendance and ratings of the intervention's efficacy, appropriateness of fit, and ease of use in daily life. All scale scores ranged from 0=completely disagree to 4=completely agree. Intervention acceptability also served as a primary outcome and was assessed via participant ratings of intervention satisfaction and liking. Of the seven participants who remained in treatment beyond the first session, an average of 8.71 (SD= 1.49) treatment sessions were attended. At the 3-month follow-up visit, participant average ratings of the intervention's efficacy, appropriateness, ease of use, and acceptability were 3.19 (SD=0.52), 2.87 (SD=0.75), 1.58 (SD=0.32), and 3.52 (SD=0.31), respectively. While the intervention was high in efficacy, appropriateness, and acceptability, these initial results suggest the intervention was not perceived as being easily integrated into participant's daily lives. With this in mind, an intervention protocol modified for predominantly remote instruction may facilitate in addressing this previous feasibility limitations (see Feasibility section 4.3C for further detail).

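### Minor, exploratory analysis only: in a single arm, correlating baseline distress with the distress outcome cannot show that distressed smokers benefit more

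*Combined protocol and SAP*

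**What the plan says.** The last paragraph under Aim 2.b in section 1.6 correlates baseline distress ratings with key outcomes. It names three kinds: feasibility and acceptability ratings, smoking change, and distress. The end of that sentence gives the purpose: "changes in smoking behavior, and emotional distress to evaluate whether the intervention may be particularly beneficial for smokers with elevated emotional distress".

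Section 6.5 repeats the plan: "we will examine correlations between baseline emotional distress ratings and key outcomes, including feasibility and acceptability ratings, changes in smoking behavior, and emotional distress". It introduces it more cautiously: "To explore whether the intervention may be particularly beneficial for smokers with elevated emotional distress".

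Neither section says whether the distress outcome is the change from baseline or the follow-up score. The outcome table in section 1.6 favours change, since its heading is "2.b: Changes in emotional distress (i.e., anxiety, depression, and stress", and the paired t-tests just above the paragraph also concern change. Neither section states how the correlations may be interpreted, and neither gives a test, an alpha or a decision rule for them.

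There is no comparison group. Section 1.1 says: "The present investigation is an open pilot trial assessing the acceptability and feasibility". Section 1.3 gives counselling and patches to everyone: "All participants will receive six smoking cessation counseling sessions" and "Participants will receive an 8-week supply of transdermal Nicotine Replacement Therapy (NRT) patches".

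**The concern.** A change score contains the baseline score with a minus sign. Someone who scores high at baseline partly through error or a bad week will tend to score lower later, whatever the treatment does. Correlating baseline with change therefore builds in a negative association, and a negative association is what a reader would take as greater benefit in distressed smokers. The pattern expected with no differential benefit looks like support for it.

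The second problem is separate. Even an outcome that does not share the baseline distress score, such as smoking change, shows within one arm only which participants improved. It does not show how they would have fared without the treatment.

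The question matters to the programme. Section 1.2 motivates the treatment by smokers with moderate emotional distress, yet the inclusion criteria in section 4.1 do not require distress. This correlation is the only analysis in 1.6 and 6.5 that addresses that subgroup. What is at stake is how one exploratory result is read when the later trial is planned.

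**Working it through.** **Inputs from the documents.** One arm and a planned n of 30 (sections 1.1 and 1.5). The plan gives no figure for this analysis, so there is nothing to reproduce. The alpha of 0.25 and d = 0.40 in section 1.5 belong to the paired t-tests.

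**Assumptions.** Baseline-to-follow-up correlation ρ = 0.5, 0.7, 0.8 or 0.9; equal SDs; the same true change in everyone; independent measurement error.

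**Step 1: sign.** Let baseline X = T + e₁ and follow-up Y = T + δ + e₂, where T is the true score and δ is the common change. Then Y − X = δ + e₂ − e₁, and Cov(X, Y − X) = −Var(e₁). This is negative whenever baseline is measured with error, however large the follow-up error is. As a check, doubling the follow-up error SD in simulation still gave mean correlations of −0.31 to −0.14.

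**Step 2: size on the change reading.** With common SD s, Cov(X, Y − X) = (ρ − 1)s² and SD(Y − X) = s√(2(1 − ρ)). The correlation is therefore −√((1 − ρ)/2):

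| ρ (assumed) | (1 − ρ)/2 | Expected r |
|---|---|---|
| 0.5 | 0.25 | −0.50 |
| 0.7 | 0.15 | −0.39 |
| 0.8 | 0.10 | −0.32 |
| 0.9 | 0.05 | −0.22 |

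**Step 3: how often the sample r is negative at n = 30.** A simulation of 40,000 trials per cell (normal true score plus independent error, common change of −0.4 SD) gave 0.998, 0.983, 0.959 and 0.887. Fisher's z approximation, Φ(atanh|r| × √(n − 3)) with √27 = 5.196, agrees closely:
- ρ = 0.5: 0.549 × 5.196 = 2.85, giving 0.998
- ρ = 0.7: 0.409 × 5.196 = 2.12, giving 0.983
- ρ = 0.8: 0.327 × 5.196 = 1.70, giving 0.956
- ρ = 0.9: 0.228 × 5.196 = 1.18, giving 0.881

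These are frequencies of the sign alone, so no test is needed for them to apply.

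**Step 4: the follow-up-level reading.** Under the same assumptions the expected correlation is simply ρ, so +0.5 to +0.9 here. It is large because scores are stable. Differential response would also move it, but one correlation cannot separate the two.

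**Step 5: smoking change.** Baseline distress is not a component of smoking change, so steps 1 to 3 do not apply. The lack of a comparator still does.

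**The case against.** The strongest reply is that the analysis is openly exploratory and worded cautiously, and that no primary or listed secondary outcome depends on it. Section 1.5 ties the decision on a larger trial to effect sizes discussed with the paired tests, not to this correlation. The results-reporting plan in section 6.4 also promises limitations and caveats in general terms. All of this stands and is why the point is minor. It does not remove the point, because an exploratory label does not tell the reader that the expected value under no differential benefit is negative.

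A reader might infer three stronger things that the documents do not support.

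- That all the planned correlations are unsound. Those with feasibility and acceptability ratings ask whether distressed smokers find the treatment usable and acceptable. One arm can describe that, and it is close to the trial's primary aim.
- That the plan carries a known false-positive rate. It specifies no test for these correlations, and the 0.25 in section 1.5 cannot be carried over to them.
- That counselling and patches confound an effect of biofeedback. The plan's use of the word intervention is mixed: it covers the combined package in some places and the breathing component in others. On the package reading, counselling and patches are part of what is studied. The missing comparator limits a causal reading either way.

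**Conclusion.** The concern holds as a minor point about one exploratory analysis. On the likelier change reading, regression to the mean alone gives an expected correlation of −0.50 to −0.22 for ρ from 0.5 to 0.9, and at n = 30 a negative sample value in about 99.8% to 89% of trials, with no differential benefit present. The negative sign rests on identical true change and independent error. The sizes also rest on equal SDs and on the assumed ρ, for which the documents give no value. On the level reading the correlation mainly reflects stability and cannot isolate differential response. On either reading, one arm shows who improved on distress or smoking, not who improved because of the treatment.

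**What to change.** Amend sections 1.6 and 6.5 in the same way:

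- **(a) Distress outcome.** State whether it is change or follow-up level. Do not use its correlation with baseline distress as evidence of greater benefit in distressed smokers. If it is reported, label it descriptive, state that regression to the mean alone is expected to make the change correlation negative, and give the baseline and follow-up SDs.
- **(b) One arm.** State that, without a comparator, the correlations with smoking change and with distress describe who improved. Leave the differential-benefit question to a baseline-by-arm comparison in the planned randomised trial.

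The correlations with feasibility and acceptability ratings need no change beyond being presented as description.

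The cost is a few sentences in each section and SDs computed from data already being collected, with no new visits or measures. The trial gives up a differential-benefit reading that one arm cannot support.
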